## **Material and methods**

### ***Study population:***

This study included 26 children with fulminant hepatitis A. They were recruited over a period of 4 years duration and divided into two groups. Group one is comprised of 18 children with fulminant HAV infection who received steroid therapy beside standard supportive measures (steroid group). The second group is comprised of 15 children with fulminant HAV infection who did not receive steroid therapy, but only standard supportive measures (non steroid group). All cases were recruited from the department of Pediatric Hepatology, Gastroenterology and Nutrition, National Liver Institute, Menofiya University. Those patients whose parents accepted to receive steroids were allocated in the steroids group; others were allocated in the control group. From each group a random sample was chosen using SPSS. An informed consent was signed by the parents of the steroid-treated patients before recruitment in the study which was approved by the Research Ethics Committee of National Liver Institute.

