### ***Outcome assessment***

The parameters of the primary response were improvement of PT followed by improvement of alanine transaminase and aspartate transaminase together with decreasing bilirubin during the period of observation. The overall clinical outcome (recovery or death) was

considered secondary response parameter. Treatment tolerability and side effects were also monitored.

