### ***Statistical analysis plan (SAP)***

Quantitative data were presented as mean  $\pm$  standard deviation (SD) while qualitative data were presented as number and percentage. For both homogenously distributed and non homogenously distributed quantitative data, significance was tested by either independent samples *t*-test or by Mann-Whitney U test, respectively. Chi-square test or Fisher's exact test was used for the measurement of the qualitative data significance. Significance was set at *P* value  $< 0.05$ . A stepwise regression analysis was performed to examine independent factors associated with the outcome. Standardized regression coefficient ( $\beta$ ), 95% confidence interval (CI) and *P* values of each independent factor are presented. Statistical analysis was performed using SPSS, version 13 (SPSS Inc, Chicago, IL, USA).

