## Results

**Table 1:** Outcome of steroid therapy

Characteristics	Steroid (n = 18)	Non-Steroid (n = 15)	P-value
Type of steroids			
Methylprednisolone	10 (55.6)	--	
Prednisolone	8 (44.4)	--	
Duration of steroids (days)			
Minimum-Maximum (median)	5 – 50 (22)	--	
Outcome			
Living	15 (83.3)	4 (26.7)	0.001
Dead	3 (16.7)	11 (73.3)	

[figure not shown]
Number of living patients were significantly higher in the steroid group compared to non-steroid group

**Table 2:** Stepwise regression analysis for parameters with significance between living and dead patients

Characteristics	$\beta$	P-value	95% CI	
			Lower	Upper
Steroid therapy	0.571	0.001	0.268	0.865
Prothrombin time (seconds)	NI	--	--	--

$\beta$ : regression coefficient; CI: confidence interval; NI: not included

Steroid therapy was the only independent parameter associated with survival of patients

**Figure 1.** Serial changes of prothrombin time (A) and total bilirubin (B) in the steroid group.

PT: prothrombin time

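### The primary response rests on four laboratory parameters with no any/all rule, assessment time or multiplicity control, so the 5% level is not guaranteed for it

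*Combined protocol and SAP*

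**What the plan says.** Under Outcome assessment the primary endpoint is described in one sentence: "The parameters of the primary response were improvement of PT followed by improvement of alanine transaminase and aspartate transaminase", and then "together with decreasing bilirubin during the period of observation". Prothrombin time (PT), ALT, AST and bilirubin thus all carry the primary label. No size of improvement, assessment day or number of parameters that must improve is given. Recovery or death is placed second: "The overall clinical outcome (recovery or death) was" classed as a secondary parameter.

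The SAP section is generic. For quantitative data, "significance was tested by either independent samples *t*-test or by Mann-Whitney U test, respectively", the choice depending on the distribution. "Significance was set at" a P value below 0.05. No endpoint is named, and there is no testing order, joint criterion or multiplicity adjustment.

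In the Results section, the visible display of primary parameters is Figure 1, captioned "Serial changes of prothrombin time (A) and total bilirubin (B) in the steroid group". Tables 1 and 2 contain no between-group P value for the change in any of the four. Part of the document was not available to me, so I make no claim about tests reported there.

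**The concern.** A 5% threshold protects a primary conclusion only if the reader knows what has to be significant for that conclusion to be drawn. Here four measures share the primary label and the only stated rule is a general cut-off for P values. Nothing prevents each of the four being compared between groups at 0.05 and a single significant one being presented as a primary response. Under that rule the error rate for the primary question would exceed 5%.

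The open observation period makes this worse. With no fixed day, the time of comparison is also free, which could give further chances of a false positive.

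**Working it through.** **Inputs**

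- Threshold 0.05, from the SAP section.
- Four primary parameters, from Outcome assessment.
- Groups of 18 and 15, from Study population and Table 1. They are used only in the simulation. The same section gives a total of 26, which is not 18 + 15 = 33, but the error rates below hardly depend on group size.
- Two-sided tests: an assumption, since the SAP does not state sidedness.
- Correlations between parameters: assumptions, shown as a range.

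**Step 1. The plan's own figure.** The 0.05 is a chosen threshold, and the documents give no family-wise error rate to reproduce. One test at this threshold has an error rate of 0.05.

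**Step 2. Any one of four suffices, independent parameters.** The chance of at least one false positive is 1 − (1 − 0.05)^4 = 1 − 0.8145 = 0.1855, or 0.1855 / 0.05 = 3.7 times the nominal level. Whatever the correlation, it cannot exceed 4 × 0.05 = 0.20.

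**Step 3. Any one of four suffices, equal correlation r.** With c = 1.96, and φ and Φ the standard normal density and distribution function, the rate is

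1 − ∫ φ(u) [Φ((c − √r·u)/√(1 − r)) − Φ((−c − √r·u)/√(1 − r))]^4 du.

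The table gives this integral beside simulated t-tests with 18 v 15 children and no true effect.

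| Assumed r | Integral | Simulation | Integral / 0.05 |
|---|---|---|---|
| 0 | 0.1855 | 0.187 | 3.7 |
| 0.3 | 0.174 | 0.176 | 3.5 |
| 0.5 | 0.156 | 0.159 | 3.1 |
| 0.7 | 0.130 | 0.130 | 2.6 |
| 0.9 | 0.094 | 0.095 | 1.9 |

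**Step 4. ALT and AST closely linked.** With an assumed ALT–AST correlation of 0.9, the rate is 0.153 if the other pairs are at 0.3 and 0.141 if they are at 0.5.

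**Step 5. Other decision rules.**

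- All four required: a false claim needs every test to be significant, so the rate is at most 0.05. With no effect on any parameter it is far lower: 0.05^4 = 0.00000625 under independence, and 0.0006 and 0.0024 in the two settings of step 4.
- PT must be significant first: with no effect on any parameter, no claim is possible unless PT gives a false positive, so the rate is at most 0.05.
- A gate alone does not protect the other three if PT truly improves. Testing them uncorrected then carries up to 1 − 0.95^3 = 0.143 under independence, so they need a correction of their own.

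**Step 6. Repeated measurement.** The number and timing of assessments are not stated, so any further inflation cannot be calculated. The figures above are for one assessment time.

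**The case against.** The strongest reply is that the text does not describe an any-of-four rule. The response is named in the singular, and the connecting words put PT first, the enzymes next, and bilirubin alongside. That fits a sequence or a joint response at least as well as four separate endpoints, and under either the error rate stays at or below 5% (step 5). This stands as a limit on the size of the problem. It does not close the gap, because the SAP section contains no gate, responder definition or all-four criterion. The wording may equally describe only the clinical order of recovery, which is not a testing rule.

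A reader might go further and infer that each parameter is tested separately at 0.05 and that the false-positive rate is therefore about three times the stated level. The documents do not support either step. The SAP sentence is a general threshold that names no endpoint, and the available results give no between-group test of any of the four. The factor of three needs both the any-of-four rule and assumed correlations near 0.5 to 0.6, or a close ALT–AST link. Nor does any section plan tests by day, so extra chances from serial values are a possibility and not a finding.

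Two more points are fair. Results are already attached, so a rule added now cannot protect an error rate in retrospect. And groups were formed by parental acceptance of steroids, so the nominal level is open to bias whatever is done about multiplicity. Both limit what the fix can achieve; neither supplies the missing rule.

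**Conclusion.** The point holds in conditional form. Four parameters are primary, the decision rule is unstated, and one uncorrected threshold is given, so the 5% level cannot be relied on for the primary response. The excess arises only if any single significant parameter may count as success. In that case the rate is about 19% under independence, falling to 16%, 13% and 9% at correlations of 0.5, 0.7 and 0.9. Under a PT gate or an all-four rule, the chance of a false primary response when nothing has an effect is at most 5%. The estimates assume two-sided tests, one assessment time and correlations that the documents do not give. This should be corrected, but it is not evidence that a false positive has been reported.

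**What to change.** State in Outcome assessment and the SAP that PT is the single primary parameter, compared between groups two-sided at 0.05 at one named assessment time. Only if PT is significant, test ALT, AST and bilirubin with Holm's correction at 0.05: the smallest P value is compared with 0.05/3 = 0.0167, the next with 0.05/2 = 0.025, the last with 0.05, stopping at the first failure. If PT is not significant, report those three descriptively.

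This holds the overall error at 0.05 in both cases. If PT has no effect, the gate limits it; if PT has an effect, Holm limits it among the other three.

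Because results are already attached, label the hierarchy as post hoc. The alternative is to report all four as between-group estimates with confidence intervals and make no confirmatory claim.

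The change takes a few sentences and the choice of an assessment time. The PT test keeps its full 0.05 and loses no power. The cost falls on ALT, AST and bilirubin, which face stricter thresholds and cannot support a claim if PT fails.

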# STUDY PROTOCOL

## Background

Fulminant hepatic failure (FHF) (alternatively, acute liver failure [ALF]) is a rare but life-threatening critical illness that occurs most often in patients who do not have a preexisting liver disease. It is the clinical manifestation of liver cell death of a critical degree with insufficient hepatocellular regeneration and is characterized by hepatic encephalopathy and/or coagulopathy. The mortality rate without liver transplantation (LT) is over 40% in patients with acetaminophen-induced FHF and 80% in those with nonacetaminophen-related FHF. This 80% decreases to 30% when LT and artificial liver support system are available. Hepatitis A virus (HAV) is considered to be the commonest cause of acute viral hepatitis worldwide. In acute infection with HAV, a cellular immune response attacking virus-infected cells is responsible for the clinical manifestations and the recovery mediated by CD8+ T cells and CD4+ T cells, in addition to B cell response producing immunoglobulin [Ig]M and IgG according to the time-course of the disease. HAV infection can cause FHF and death in about 0.2% of clinical cases. Extensive destruction of infected hepatocytes by T cell-mediated lysis was supposed to be the cause of FHF. Hepatitis A virus (HAV) is the most common cause of acute viral hepatitis worldwide. In acute HAV infection, a cellular immune response attacking virus-infected cells is responsible for the clinical manifestations and the recovery mediated by CD8+ T cells and CD4+ T cells, in addition to B cell response producing immunoglobulin [Ig]M and IgG according to the time-course of the disease. Although rare, HAV infection can cause FHF and death in approximately 0.2% of clinical cases. Overwhelming elimination of infected hepatocytes by T cell-mediated lysis was supposed to be the cause of FHF.

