### ***Treatment regimen and modifications***

Patients were initially assigned to receive prednisolone at a dose of 1 mg/kg/d or its equivalent dose of methylprednisolone (0.8 mg/kg/d) for those who cannot take oral prednisolone (as patients with encephalopathy or vomiting). In those with improved PT (while on steroid therapy) below 20 seconds in conscious patients or below 15 seconds in encephalopathic patients, the steroid dose was maintained for further two weeks then withdrawal started. In those who had deterioration of liver functions upon withdrawal, treatment was continued for a longer duration till satisfactory biochemical improvement was achieved. The treatment was scheduled to be discontinued if uncontrollable hyperglycemia, gastrointestinal bleeding, or brain edema develops.

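### Harms are undefined and named only as reasons to stop the steroid, with no stated provision for the same count in controls, so no comparative or causal tolerability conclusion is supported

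*Combined protocol and SAP*

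**What the plan says.** The harm outcome is one sentence in Outcome assessment: "Treatment tolerability and side effects were also monitored". It gives no event list, definition, time window, group or method of comparison.

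Specific harms are named only under Treatment regimen and modifications: "The treatment was scheduled to be discontinued if uncontrollable hyperglycemia, gastrointestinal bleeding, or brain edema develops". The treatment meant there is the steroid.

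The statistical analysis plan gives general tests for qualitative data and does not mention harms. In Results, Table 1 ("Outcome of steroid therapy") reports steroid type, steroid duration and survival; Table 2 reports a regression. Neither gives a harm count for either group or a reason for stopping a steroid course.

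Background says that the disease "is characterized by hepatic encephalopathy and/or coagulopathy", and the case definition under Etiological diagnosis and group allocation builds entry on the same two features. Allocation was not randomised: "Those patients whose parents accepted to receive steroids were allocated in the steroids group".

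**The concern.** A control child has no steroid to stop, so the three named events have no stated role in that group. The natural reading is a harm measure for one group. If harms are collected that way, a bleed or an episode of brain edema on steroids cannot be assigned to the drug rather than the disease, and neither an excess nor a deficit against supportive care can be seen.

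The tables present a large survival difference in favour of steroids in critically ill children. Readers will want to weigh that against non-fatal harm, and the available text gives them nothing to weigh. Consent is described for parents of steroid-treated children only, and Figure 1 shows serial laboratory values for the steroid group only. Both make uneven collection of harms plausible, though neither proves it.

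**Working it through.** **Inputs.** Group sizes are 18 and 15 (Study population: "Group one is comprised of 18 children with fulminant HAV infection who received steroid therapy"; "The second group is comprised of 15 children with fulminant HAV infection who did not receive steroid therapy"). The same section also says "This study included 26 children with fulminant hepatitis A", while 18 + 15 = 33, so the denominator for any harm rate needs to be settled; 18 and 15 are used here because Table 1 uses them. Deaths are 3/18 (16.7%) and 11/15 (73.3%), from Table 1. Harm rates are not given for either group; every harm count or rate below is hypothetical.

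**The plan's own figure.** There is no harm figure to reproduce. The survival comparison, 15/18 against 4/15, reproduces: uncorrected chi-square = 10.76, P = 0.00104, against the stated 0.001. Nothing below depends on it.

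**Step 1: what the steroid group alone can show.** The exact (Clopper-Pearson) 95% limits for x events in n = 18 are the 0.025 quantile of Beta(x, n - x + 1) and the 0.975 quantile of Beta(x + 1, n - x). For x = 0 the upper limit reduces to 1 - 0.025^(1/18) = 18.5% (one-sided: 1 - 0.05^(1/18) = 15.3%).

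| Events in 18 | 95% interval |
|---|---|
| 0 | 0% to 18.5% |
| 2 | 1.4% to 34.7% |
| 4 | 6.4% to 47.6% |

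**Step 2: how far the meaning depends on the control count.** Suppose 4 of 18 steroid-treated children had an event (22.2%). The difference is 4/18 - b/15 for b control events, with two-sided Fisher P:

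| Control events (b of 15) | Difference (points) | P |
|---|---|---|
| 0 | +22 | 0.11 |
| 3 | +2 | 1.00 |
| 5 | -11 | 0.70 |
| 8 | -31 | 0.08 |

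The same steroid-group count can suggest harm, no difference or protection. The sign is set by the number that the plan does not say it will collect.

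**Step 3: what a two-group count could deliver.** Power of the two-sided Fisher test at 0.05 for 18 against 15, by full enumeration, over assumed control rates of 5% to 40% (the plan does not state sidedness; two-sided is assumed):

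| Excess on steroids | Power |
|---|---|
| 10 points | 6% to 8% |
| 20 points | 17% to 28% |
| 30 points | 35% to 56% |
| 40 points | 60% to 79% |

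A control count gives an estimated difference with an interval, but could not show that the steroid is safe.

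**Step 4: time at risk.** With deaths of 73.3% in controls and 16.7% on steroids, controls probably had less time in which to record a non-fatal event. Raw counts would then tend to understate the control rate, so death has to be treated as a competing event.

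**Step 5: stopping reasons.** Table 1 gives a minimum steroid duration of 5 days. Treatment regimen and modifications keeps a child whose prothrombin time has improved on the dose for two more weeks (14 days) before withdrawal begins. Since 5 < 14, at least one course ended before that schedule could be completed. Death or stopping for harm could each explain it; Table 1 does not say which.

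**The case against.** The strongest reply is that the plan is silent on control monitoring and does not exclude it. The harm sentence names no group, controls were also treated (with supportive care), and the planned chi-square or Fisher tests could serve a two-group harm comparison. A reader might infer that controls were not monitored; the documents do not say so. This stands, and statements of absence here cover only the text available.

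A reader might also take it as documented that bleeding and brain edema are complications of this disease. The documents name only coagulopathy and encephalopathy; the overlap is a plausible inference from these. It does not extend to hyperglycemia, the third named event.

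A reader might conclude that nothing can be said about tolerability, or that no comparative safety figure exists. Both go too far. Event counts and stopped courses in the steroid group, with intervals, are a legitimate description. Death is reported in both groups, so a fatal bleed or fatal brain edema is already inside a two-group figure. What is missing is the comparison of non-fatal and cause-specific harm. The available text also draws no safety conclusion of its own.

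Finally, 18.5% is a property of any group of 18, not a defect peculiar to this trial. That is correct: it shows only that an absence of events would not settle the matter.

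These replies limit the wording but do not close the gap. Nothing available provides for identical collection, and the tables show no sign that it was done.

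**Conclusion.** The point holds in a limited form and should be acted on. Harms are undefined, the named events are tied only to stopping the steroid, identical collection in controls is not provided for in the available text, and no harm count or stopping reason is reported. A steroid-group count would support a within-group description but no comparative or causal tolerability conclusion. Zero events in 18 would still be compatible with a rate of up to 18.5%, and a hypothetical 4 of 18 could lie 22 points above or 31 points below controls, depending on their count.

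This rests on two assumptions: that the harm sentence refers to steroid treatment, as the usage in Treatment regimen and modifications suggests, and that bleeding and brain edema have a background rate above zero without steroids. A control count is necessary for a comparison but not sufficient. Parental choice of treatment, unequal time at risk and groups of 18 and 15 would leave it confounded and imprecise.

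**What to change.** Make harm a two-group outcome:

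- Count gastrointestinal bleeding, brain edema, hyperglycemia and infection in both groups from enrolment, by the same definitions and over the same observation window, regardless of perceived relation to the steroid. Infection is not named in the documents; it is added for completeness of the harm record.
- Beside survival, report counts per group with exact 95% intervals and time at risk, treating death (3/18 and 11/15) as a competing event.
- Report the number of steroid courses stopped for each reason.
- State that allocation by parental choice and groups of this size leave the comparison confounded and imprecise, so that it cannot establish safety.
- If control events cannot be retrieved, limit the report to a within-group description and say so.

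This alters no treatment or stopping rule. The cost is some chart abstraction and a few table rows, on the assumption that the charts record these events. Because consent is described only for parents of steroid-treated children, the sponsor should check whether abstracting further control data needs approval. The downside is wide intervals and possibly a less favourable safety statement.

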### ***Statistical analysis plan (SAP)***

Quantitative data were presented as mean  $\pm$  standard deviation (SD) while qualitative data were presented as number and percentage. For both homogenously distributed and non homogenously distributed quantitative data, significance was tested by either independent samples *t*-test or by Mann-Whitney U test, respectively. Chi-square test or Fisher's exact test was used for the measurement of the qualitative data significance. Significance was set at *P* value  $< 0.05$ . A stepwise regression analysis was performed to examine independent factors associated with the outcome. Standardized regression coefficient ( $\beta$ ), 95% confidence interval (CI) and *P* values of each independent factor are presented. Statistical analysis was performed using SPSS, version 13 (SPSS Inc, Chicago, IL, USA).

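### The primary laboratory response is compared only by unadjusted group tests, so in groups formed by parental choice any difference in entry PT, ALT, AST or bilirubin can pass into the result

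*Combined protocol and SAP*

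**What the plan says.** Under Outcome assessment: "The parameters of the primary response were improvement of PT followed by improvement of alanine transaminase and aspartate transaminase together with decreasing bilirubin". No assessment day is given, and nothing says whether final values, changes or a yes/no criterion are compared. Recovery or death is secondary.

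Under Statistical analysis plan (SAP): "For both homogenously distributed and non homogenously distributed quantitative data, significance was tested by either independent samples" t-test or Mann-Whitney U test. Qualitative data go to chi-square or Fisher's exact test. No entry value appears as a covariate in any of these. The one multivariable analysis is a stepwise regression on the outcome, which Table 2 in Results shows to be living versus dead.

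Under Study population, allocation was not random: "Those patients whose parents accepted to receive steroids were allocated in the steroids group; others were allocated in the control group". The sentence that follows, "From each group a random sample was chosen using SPSS", describes sampling within groups that already existed. The group sizes are given as "Group one is comprised of 18 children with fulminant HAV infection who received steroid therapy" and "The second group is comprised of 15 children with fulminant HAV infection who did not receive steroid therapy".

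The only laboratory course visible in Results is Figure 1: "Serial changes of prothrombin time (A) and total bilirubin (B) in the steroid group".

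**The concern.** Improvement is judged against where the child started. A between-group test that ignores the starting value is safe on average when allocation is random. Here families chose, and drawing a random sample inside each chosen group does nothing to balance the two. Equal entry values cannot be taken for granted.

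Higher values are worse for all four laboratory measures. If one group entered less ill, a test on follow-up values tends to credit that group with a better response. If values in both groups drift towards a common mean, a test on raw change errs the other way, because the sicker group has further to fall. The plan does not say which of the two is tested, so even the direction of a possible bias is open.

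At stake are the error rate of the primary comparison and, with only 33 children, some precision.

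**Working it through.** **1. Does the stepwise regression adjust the laboratory response?** Table 1 gives 15 of 18 living v 4 of 15.
- Pearson chi-square = 33 × (15×11 − 3×4)² / (18×15×19×14) = 772,497 / 71,820 = 10.76, P = 0.001, as printed.
- Phi = √(10.76/33) = 0.571, the printed coefficient.
- Least-squares slope of alive (1/0) on steroid (1/0) = 0.833 − 0.267 = 0.567, 95% CI 0.268 to 0.865, which is the printed interval.

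Table 2 is therefore a linear regression of survival on steroid alone. PT was not retained. It adjusts no laboratory response.

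**2. Inputs for the error-rate check**
- From the documents: group sizes 18 and 15. The stated total of 26 conflicts with 18 + 15 = 33; Table 1 uses 18 and 15. Significance level 0.05, taken as two-sided because the SAP does not say.
- Assumed, because the documents give no figure: entry difference d = 0.5 to 0.8 SD, entry-to-follow-up correlation r = 0.5 to 0.7, normal values with unit SD, and every child measured at follow-up.

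**3. Expected false difference with no treatment effect**

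| Analysis | Groups regress to a common mean | Groups keep a stable difference |
|---|---|---|
| Follow-up value | r × d | d |
| Change | −(1 − r) × d | 0 |
| ANCOVA | 0 | (1 − r) × d |

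Example, d = 0.5 and r = 0.5, common mean: +0.25 SD on follow-up values, −0.25 SD on change, 0 for ANCOVA.

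**4. Rejection rates** (simulation, 40,000 trials per row; follow-up t-test / change t-test / ANCOVA)

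| d | r | Common mean | Stable difference |
|---|---|---|---|
| 0.5 | 0.5 | 10.6 / 10.5 / 5.0% | 28.3 / 5.2 / 12.0% |
| 0.5 | 0.7 | 16.4 / 8.1 / 4.9% | 28.8 / 5.0 / 8.8% |
| 0.8 | 0.5 | 19.6 / 19.7 / 5.0% | 60.6 / 5.1 / 22.0% |
| 0.8 | 0.7 | 34.2 / 13.8 / 5.0% | 60.0 / 5.2 / 13.7% |

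Separate runs agree to within one or two percentage points; they put the highest ANCOVA figure between 21% and 23%. Mann-Whitney on follow-up values, common mean, rejects in 11% to 32%, so the alternative test gives no protection.

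**5. Precision when entry values are equal.** Adjustment removes r² of the follow-up variance: 0.5² = 25% to 0.7² = 49%. Against the change score, whose variance is 2(1 − r), the saving is 1 − 0.75/1.00 = 25% at r = 0.5 and 1 − 0.51/0.60 = 15% at r = 0.7.

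**6. Values lost through death.** Table 1: 11/15 v 3/18 died. Timing is not given. If every death came before the assessment day, 15 v 4 children would remain. In that extreme, with equal entry values and no laboratory effect, ANCOVA rejects in 5% to 6% of trials if death and the laboratory value correlate at 0.25, 8% to 10% at 0.5 and 14% to 17% at 0.7 (assumed correlations).

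**The case against.** **The test is not named.** The SAP sentence is generic and assigns no test to the primary response. The treatment section uses PT thresholds, so a yes/no reading of improvement is possible. This stands. It changes which test applies but not the gap, since chi-square and Fisher's exact are equally unadjusted. The t-test error rates and the log-scale ANCOVA would not carry over directly to that reading.

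**No imbalance is shown.** The available text has no entry values by group, and some pages were not available, so their absence proves nothing. This stands. A reader might infer that the laboratory comparison is in fact biased, or biased in favour of steroids. The documents support neither, and the 0.5 to 0.8 SD range is an assumption.

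**ANCOVA is not a guarantee.** It holds 5% only when group matters solely through the measured entry value. If the two kinds of family differ by a stable amount, the change score holds 5% and ANCOVA does not. This stands. A reader might conclude that every unadjusted analysis loses its error rate, or that adjustment restores it. Both statements depend on which pattern applies, and the documents do not settle that.

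**Serial values.** A reader might infer that independent-samples tests were applied to repeated values from the same child. The plan does not say so, and the Figure 1 caption reports no test.

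**The endpoint comes first.** An ANCOVA needs an assessment day and control-group values; the first is undefined and the second are not shown. This is fair as to order. It does not remove the need for an entry covariate once the day is fixed.

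**Conclusion.** The concern holds in this form: every group test planned for the primary laboratory response is unadjusted, allocation followed parental choice, and the only regression concerns survival. Entry differences can therefore pass into the result.

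The size is conditional on the assumed d and r and on complete follow-up. With regression to a common mean, unadjusted t-tests reject a true null in about 11% to 34% of trials on follow-up values and 8% to 20% on change, against about 5% for ANCOVA. With a stable group difference, follow-up tests reject in about 28% to 61% and ANCOVA in about 9% to 22%, while the change test holds 5%. In both patterns ANCOVA does better than the unadjusted test on follow-up values; it does not always do better than the change score.

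The change should be made, but it does not make the comparison causal. Unmeasured differences between families who accepted and refused steroids remain, and so does selection by death.

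**What to change.** - Fix the assessment day and the scale of the endpoint in the SAP.
- Make the primary comparison for PT, ALT, AST and bilirubin an ANCOVA on the log value, with the child's own pre-treatment log value as covariate. If several days are used, fit a mixed model with a random child effect and the same covariate. Report the adjusted ratio with its 95% CI.
- Add a change-score analysis as a sensitivity analysis. If it and the ANCOVA disagree, report both and say that the conclusion depends on how entry differences are assumed to evolve.
- Report entry values by group, and the number of children per group with a value at the assessment day.
- Add a sensitivity analysis that ranks death as the worst laboratory outcome. A mixed model does not by itself solve truncation by death.
- State that adjustment removes only confounding through measured entry values.

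Cost: SAP wording, one degree of freedom per model for the entry covariate, and a re-run, provided that control-group laboratory values are on file. The available text shows serial values for the steroid group only, so that has to be confirmed first.
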